In order to better understand treatment mechanisms, and possibly predict long-term outcomes, we propose concurrently to explore Specific Aim 1 (1.1, 1.2, and 1.3) exploratory potential disease biomarkers as outlined below. The primary outcome of this study is motor function rated with the Physical and Neurological Examination for Subtle Signs (PANESS), a validated scale that consistently demonstrates significant impairments in children with ADHD, and which our preliminary data suggest may demonstrate more extreme problems in children with NF1. The first exploratory biomarker is motor system inhibitory physiology, measured using Transcranial Magnetic Stimulation (TMS). Preliminary measures in our NF1 population also show abnormalities similar to established findings in ADHD. The second exploratory biomarker is metabolomics profiling for the biomarker of oligodendrocyte dysfunction in NF1 participants: autotaxin. Preliminary data in our NF1 population showed specific signal abnormalities in the NF1 population compared to healthy controls. Therefore, we propose to perform a double-blind placebo controlled, prospective, Phase IIa study to explore safety, tolerability, and efficacy of NAC on learning and motor behavior in children with NF1 aged 8 through 16 years old.

PURPOSE OF STUDY:

The aims of this application are to gain information in children with NF1 about possible clinical benefit of anti-oxidant treatment and to develop and evaluate quantitative brain-based and blood biomarkers relating to presence of NF1, symptom severity, and response to antioxidant therapy. Clinically, 50% of children with NF1 are underperforming or failing at school [1]. This frequently leads to decreased educational attainment and fewer opportunities as adults. An important first step was our preliminary work using the PANESS scale and Transcranial Magnetic Stimulation (TMS)-evoked Short Interval Cortical Inhibition (rSICI) in children with NF1. We propose to develop and extend our understanding of NF1-related motor and learning behavior in response to antioxidant therapy with NAC. The purpose of the present study is to 1) evaluate tolerability, safety, and clinical benefit of NAC in this double-blind placebo controlled study; 2) to evaluate motor function (PANESS) and physiology (TMS) biomarkers at baseline and after treatment; and 3) to quantify metabolomics profiles at baseline and after treatment. We propose to study 20 children with NF1, ages 8-16 years, at baseline and after completion of 8 weeks of treatment with NAC.

NAC therapy, if successful, is expected improve these parameters. Our trial endpoints are: Does behavior improve? Does motor function improve? Are there TMS biomarkers that reflect the presence of NF1 and the response to NAC treatment? Are there metabolomics measures that reflect the presence of NF1 and the response to treatment? We hypothesize that we can identify predictive measures as a foundation for an application for funding for a larger, more definitive, placebo-controlled trial involving biomarkers and clinical outcomes. We believe this work has the potential to lay groundwork for future use of relevant biomarkers for treatment and outcomes research for NF1 as well as other biologically similar conditions, collectively designated the "RASopathies" (due to involvement of the RAS family of proteins) and ultimately to guide development of more effective treatments based on disease pathophysiology.

SPECIFIC AIMS

This study involves the following aims:

Specific Aim 1: Primary Outcome of Study

In children and adolescents with NF1, to characterize the behavioral and motor effects of 8 weeks of N-acetylcysteine (NAC) treatment in a cohort of 20 children and adolescents with NF1. We will evaluate tolerability, safety, and clinical benefit of NAC in this double-blind crossover placebo controlled study. Aim 1.1: Characterize effects of NAC treatment on motor function in kids with NF1 using the Physical and Neurological Examination for Subtle Signs (PANESS). This is a validated scale that consistently demonstrates significant impairments in children with ADHD, and which our preliminary data suggest may demonstrate more extreme problems in children with NF1 than age-matched healthy controls (unpublished data from CCHMC). We hypothesize that motor function scores rated with the PANESS scale will improve

Version 9.0 MAR2020 Page **3** of **24**

after treatment with NAC. **Aim 1.2**: Characterize effects of NAC treatment on ADHD symptoms in children with NF1. We hypothesize that ADHD attention and hyperactive/impulsive symptoms, rated with the DuPaul DSM-5 based clinical rating scales, will improve after treatment with NAC.

Specific Aim 2: Experimental aim # 1

In the same cohort, we will identify potential novel biomarkers of neurodevelopmental burden in NF1. Aim 2.1: Describe the function and physiology of the motor system using Transcranial Magnetic Stimulation (TMS) as a possible disease biomarker of NF1. Preliminary measures in our NF1 population also show abnormalities similar to established findings in ADHD. We hypothesize that children with NF1 will have significantly less motor cortex inhibition using TMS measurements, and these measures will improve ("normalize") upon NAC treatment. We will compare to our internal age-matched healthy controls at Cincinnati Children's. Aim 2.2: We propose to evaluate autotaxin as a candidate biomarker of oligodendrocyte dysfunction in NF1 participants. Preliminary data from our biomarker discovery analysis of serum samples from healthy controls and NF1 patients showed lysophosphatidylcholine (LPC) depletion compared to healthy age/sex matched controls. In gene expression analysis autotaxin was elevated 4 times in neurofibroma Schwann cells compared to normal nerve Schwann cells. We will collect serum and plasma from participants to assess autotaxin/LPC axis prior and post-NAC therapy. We hypothesize that autotaxin axis abnormalities will be a biomarker of response to antioxidant therapy in our NF1 population.

Specific Aim 3: Experimental aim # 2

In the same cohort, to evaluate metabolomics profiles as a possible disease biomarker that is affected by NF1 and by treatment with NAC as per Aim 1. Hypothesis 4: We hypothesize that specific profiles will predict clinical response to antioxidant therapy compared to age-matched healthy control (unpublished data from CCHMC).

BACKGROUND:

Neurofibromatosis (NF1) – overview

Neurofibromatosis (NF1) is an autosomal dominant condition affecting many organs, resulting from mutations in the neurofibromin gene [2]. Characteristically, individuals with this condition have cutaneous manifestations, most prominently hyperpigmented macules termed "café-au-lait" spots. The neurofibromin gene functions in part as a tumor suppressor, and persons with NF1 are susceptible to malignant and benign tumors in multiple organs. What is less well studied is that individuals with NF1 commonly suffer from difficulties with behavioral and emotional regulation including ADHD symptoms, learning disabilities, and developmental delays in motor function [3]. These cause substantial morbidity in adulthood.

NF1 – challenges evaluating behavioral, emotional, and cognitive symptoms

Clinically, 50% of children with NF1 are underperforming or failing in school [1]. This frequently leads to decreased educational attainment and fewer opportunities as adults. The high prevalence of behavioral, emotional, and cognitive problems in persons with NF1 suggests that neurofibromin may play a role in structure and/or healthy, efficient function of the brain. Clarifying this is challenging because most likely behavioral, cognitive, and motor impairments in NF1 result, as in other genetic conditions, from multiple complex factors including environmental factors and genetic loading distinct from the major effect of mutations in neurofibromin [4]. Moreover, cognitive and behavioral symptoms are difficult to quantify. Rating scales capture impressions of parents and teachers in the important domains of home and school, but they are subjective ratings, not brain-based measures [5]. Moreover, if treatments during a clinical trial are beneficial, there may be biological changes that precede clinical ones. Measuring these changes may be important for validating treatment mechanisms and effects.

NF1 – neurobiological basis for behavioral, emotional, and cognitive symptoms and role for physiological biomarkers

Version 9.0 MAR2020 Page **4** of **24**

It has long been known that children with NF1 have enlarged heads – macrocrania. More recent reseach has shown that children and adults with NF1 often have enlarged myelin-rich white matter tracts [6]. These findings have been associated with behavioral and cognitive impairment in NF1 human studies and Nf1 animal models [7] [8]. Oligodendrocytes are the cells that make myelin in white matter tracts. Quantitative biomarkers of white matter structures may help measure and predict behavior in NF1 and facilitate interventions into clinical practice. Diffusion tensor imaging (DTI) shows global changes in NF1 participant brains which are consistent with white matter dysfunction [9]. White matter properties can also be evaluated using neurophysiological techniques, including Transcranial Magnetic Stimulation (TMS). TMS studies are generally brief, inexpensive, readily repeatable, and do not require sedation. TMS may be helpful for identifying clinically useful, specific brain biomarkers and assessments related to motor and learning difficulties in NF1 and, ultimately, other conditions involving RAS pathways (related RASopathies).

The biomarkers in Aim 2 have been developed and optimized in three NIH R01 grants. In collaboration with investigators at the Kennedy Krieger Institute in Baltimore, in studies that are ongoing, we demonstrated in a seminal publication that both the motor control assessment proposed for this study, the PANESS, and the primary physiological biomarker, TMS-evoked Short Interval Cortical Inhibition (SICI), correlate robustly with the presence and severity of ADHD [10]. We and others have also demonstrated that SICI is sensitive to medications, and, further that 4 weeks of treatment with a norepinephrine reuptake inhibitor can both improve ADHD symptoms and, in a statistically correlated way, alter TMS-evoked SICI [11]. In a preliminary study (unpublished data, see figure 2), we have evaluated these potential biomarkers in 11 children with NF1 and compared these to data in approximately 50 children with ADHD and 50 health controls. As shown in figure 2 (NF1 sample n=9 due to age matching), both motor scores with PANESS and TMS-evoked SICI appear to differ in NF1 children, with values as extreme or more extreme than those found in the ADHD cohort. Two other measures are also shown, whose differences were not significant in this study.

We have analyzed datasets from our untargeted metabolomics data for statistically significant metabolic pathways and identified abnormalities in the lysophosphatidylcholine (LPC), lysophosphatidic acid (LPA), Autotaxin axis. Autotaxin is a secreted phosphodiesterase that produces LPA from LPC. LPA is a lipokine that acts through specific guanine-nucleotide-binding protein (G protein)-coupled receptors to stimulate migration, proliferation, oxidative stress, survival and other functions in many cell types. Autotaxin has been shown to play a significant role in OLG development via 2 domains, the modulator of OLG remodeling and focal adhesion organization (MORFO) [12] and the catalytic enzyme domain that generates LPA [13]. Autotaxin is predominantly expressed and secreted in OLG cell lineage cells [14].

N-acetylcysteine (NAC) – properties, and rationale for use in NF1

We have treated 4 patients off-label with NAC at 900 mg twice daily with improved behaviors without side effects at our center and external collaborators at Children's National Medical Center. We will assess the safety and efficacy of N-acetylcysteine (NAC) in a phase II pharmacological intervention clinical trial in children with NF1. This drug choice is based on our findings from mouse models of the central nervous system manifestations of NF1, which reveal a role for myelin-forming oligodendrocytes in the control of nitric oxide synthases (NOS) and their product nitric oxide in maintenance of brain structure and function, including regulation of behavior and motor control (see below figure). Treating these mice with NAC corrected cellular and behavioral abnormalities [15] [16].

Version 9.0 MAR2020 Page **5** of **24**

[figure not shown]
[figure not shown]

Figure 1. Nitric oxide (NO) can disrupt tight junctions and gap junctions altering the surrounding vasculature. NF1 loss and Ras hyperactivation can upregulate NO and NO synthases (NOS) in white matter. Treating mice with the antioxidant Nacetyl cysteine corrected cellular phenotypes. NAC is the N-acetyl derivative of 1-cysteine. In the brain, NAC can influence oxidation. Once in the cell, the cystine is reduced to cysteine, the rate-limiting component of the endogenous antioxidant molecule glutathione.

NAC is a natural supplement that acts as an antioxidant and a glutamate modulating agent. It is widely available over the counter. Although no controlled safety studies have been published, NAC has been widely used in large doses for decades in the management of acetaminophen overdose. Its most common side effects are gastrointestinal, as noted in a recent study in children with Autism Spectrum Disorder. Relevant to this proposal, NAC was used to treat ADHD symptoms in systemic lupus erythematosus [17], Autism Spectrum Disorder (ASD), anxiety, and depression [18] [19] with promising responses [15] [16]. Dose of NAC will be used based on these prior published studies. As reported in these studies, there were no serious adverse events. Most side effects, such as nausea, were mild to moderate in severity and were transient and reversible.

Table 1: NAC Preliminary Data							
Condition	Study design	Dose	Sample size	Result	Citation		
SLE with ADHD	Randomized, Placebo	2.4 or 4.8	6 placebo, 9 each	Improved	Garcia 2013 [17]		
	controlled	gm/day	dose; adults, 3 months	ADHD			
Bipolar disorder	Open label	2 gm/day	149 adults, 2 months	Improved	Berk 2011 [20]		
				depression			
Autism Spectrum	12 week double blind	900 mg TID	14 NAC, 15 placebo,	Reduction in	Hardan 2012 [19]		
Disorder	randomized placebo		children	ABC			
	controlled			irritability			

TMS PRELIMINARY DATA: The goal of Aim 2 is to translate molecular, cellular, and animal model data to human NF1 clinical trials through evaluating human brain physiology. Our preliminary work comparing 9 NF1 children (mean IQ 94) with age-matched (all ages 8-12; mean for all groups 10.5 years) cohorts of 52 ADHD and 62 typically developing children (Figures 2a-d) has identified PANESS and TMS-evoked SICI as promising biomarkers.

Version 9.0 MAR2020 Page **6** of **24**

Figure 2. a TMS Resting Motor Threshold (RMT) $(F_{2,113} = 1.7, p = .2)$; **b** Short Interval Cortical Inhibition (SICI) $(F_{2,94} = 10.3, p = .0001)$; **c** Intracortical Facilitation (ICF) $(F_{2,97} = 1.6, p = .2)$; **d** PANESS motor function battery $(F_{2,105} = 30.3, p < .0001)$.

METABOLOMICS DATA: untargeted global metabolomics profiling is a non-invasive technique that can help identify novel biomarkers that correlate with clinical disease and response in the setting of NF1. We have successfully performed untargeted metabolomics experiments using serum from healthy controls (n=12) and NF1 patients (n=18) collected from the NF1 center in our mass spectrometry laboratory. Patients with NF1 showed a distinct metabolomics signature compared to healthy age/sex match controls (Figure 3A). This preliminary data strongly supports our hypothesis that RAS-MAPK disorders can lead to detectable biochemical abnormalities. A clinical database with patient characteristics already exists at our center. We have input plexiform neurofibroma (PNF) growth to correlate with metabolomics data (Figure 3B). This technology will allow potential identification of candidate biomarkers that could correlate with different disease complications including behavioral abnormalities. We plan to collect samples from NAC treated individuals to identify compounds that mark response to therapy, and could serve as response biomarkers in a larger Phase II trial.

[figure not shown]

Figure 3. Neurofibromatosis type 1 metabolomics pattern is different from healthy controls. **A.** Heatmap was based on 203 compounds out of 5,206 statistically significant compounds (p<0.005, fold change >2). Selected compounds includes diacylglycerol, lysophospholipids, ceramides species and other compounds. Blue indicates low abundance and Red increased abundance.

B. A principal component sub-analysis of these samples suggests a different biochemical profile and 10 candidate biomarkers in the NF1 patients who have progressive plexiform neurofibromas (PNFs) versus NF1 patients without PNFs.

- **Figure 4.** Lysophosphatidylcholine (LPC) species are depleted in serum from NF1 patients. **A.** Volcano plot for biomarker discovery (p<0.005, fold change >2) shows low abundance of LPC18:0
- fold change >2) shows low abundance of LPC18:0 and PCo18:1 in NF1 patients versus healthy controls.
- **B**. Targeted mass spectrometry analysis of LPC species confirmed low LPC18:0 in NF1 patients (NF1^a) compared to controls (p<0.005). Replication cohort showed similar differences (NF1^b). **C**. Heatmap based on LPC species (p<0.005, fold change >2). All LPC species were low in the NF1 patient cohorts versus healthy. Blue indicates low abundance and Red increased abundance.

Objective and Rationale for Aims 1-2. We propose a cross-sectional study where we will compare PANESS and SICI measures in 20 children with NF1 with data already acquired at CCHMC with those 2 measures. Next, these 20 children will be treated with NAC as described below. PANESS and TMS measures will be repeated after 8 weeks of treatment. Clinical symptom ratings will be performed independently. Motor and TMS ratings and clinical ratings will be blinded to one another until analyses are completed at the end of

Version 9.0 MAR2020 Page 8 of 24

the study. At present, there are no clinical characteristics, neuropsychologic variables, phenotypic variants or biomarkers which can accurately predict treatment response of abnormal motor/learning behaviors in NF1 to NAC therapy. We will assess ADHD attention and hyperactive/impulsive symptoms with the DuPaul DSM-5 based clinical rating scales and predict an improved rating after treatment with NAC.

Screening Period: Screen candidates will be solicited from clinic referrals and from advertisements. If, after the screening visit, the candidate is determined eligible to participate, the candidate will then be entered into the baseline testing portion of the study.

Baseline Testing Period (Visit 0): Baseline testing may occur remotely, may coincide with the first study visit, or split among both options and will consist of clinical assessments and ADHD severity testing with evaluation by an independent rater blinded to study procedures as well as parent ratings of ADHD, assessment of anxiety, and depressive symptoms. Some participants may undergo a short, optional pretreatment, unsedated research MRI for structural and DTI. All participants will receive a full psychometric and neurological examination and be screened with a comprehensive assessment battery designed to guarantee that they meet inclusion/exclusion criteria for the study, that they are candidates to receive NAC being offered in the trial, and that a robust database is available regarding NF1 motor/learning behavior symptomatology, comorbid symptomatology, broader psychosocial function, neuropsychological function, academic performance, severity and impairment, and medical status. Per FDA Guidance for Industry: Suicidal Ideation and Behavior: Prospective Assessment of Occurrence in Clinical Trials, an assessment for suicide (Columbia Suicide Severity Rating Scale, C-SSRS) will be performed at every visit and monitoring visits or phone calls.

Treatment Observation Period:

Phase I:

Study initiation will consist of motor PANESS and TMS measures (AIMS 1 and 2) and blood will be drawn for metabolomics profiles (AIM 3). Subjects will then return to the outpatient RASopathies clinic where they will be assigned to one of two treatment arms (NAC drug or placebo) of this study. Each subject will receive drug or placebo (visits 1 and 3) without feedback regarding treatment arm assignment to [name] until the end of the study. At each of these outpatient visits (visits 1 and 3) subjects will be assessed for vital signs, adverse events, pill counts and concomitant meds, and for motor/learning behaviors severity and improvement. At the final phase I and final study visits (visits 2 and 4, respectively), treatment outcomes will be rated by an independent rater as well as by the study physician ([name], or qualified designee) for motor/behavior improvement. A repeat longitudinal TMS study will occur at weeks 8 and 18 (at the end of phase I and phase II, respectively) while on a stable treatment dose of NAC or placebo (visits 2 and 4) by [name] within 8-10 hours following AM dosing. At end of the final phase I study visit (visit 2), subjects will undergo an 'interphase' for 1 week during which they will abstain from medication (drug or placebo). After interphase, subjects will enter phase two of this cross-over double-blind placebo controlled study and commence the alternative treatment arm.

Phase II:

In phase two, subjects will cross over to the opposite treatment arm (NAC drug or placebo) than they were assigned during phase one. All other details outlined in phase I will remain unchanged.

After both phases of the treatment observation period are complete, there will be a debriefing interview, in which children and their families will review both their performance during the trial and tolerability data (visit 5). A plan for follow-up care will be created by [name], or qualified designee, with referral for follow-up treatment. If needed, subjects will be given transition medication (atomoxetine or otherwise depending on effectiveness of study drug) until subject can establish appropriate care with a clinician.

Version 9.0 MAR2020 Page **9** of **24**

Emergency Study Extension

In light of the recent coronavirus pandemic, CCHMC has implemented significant restrictions on in-clinic study visits and other non-essential activities that prohibit normal operations. Below is a two-option contingency plan to accommodate currently enrolled and active (on drug/placebo) participants (all are currently in phase II of the study, between week 14 and 18).

Contingency Option 1:

Study participants whom are currently enrolled and on study drug (or placebo) are to maintain a stable dose (no change in dose). At week 18, when an in-person study visit would typically occur, a virtual visit will take place. This week 18 virtual visit can occur over the telephone, via email, or videoconference. Virtual assessments will include surveys and PANESS (performed via videoconference when possible).

After the in-clinic study visit restrictions have been lifted all study visit assessments will be performed as outlined in this protocol. If restrictions to hospital access are still in place at week 26 (8 weeks after the originally-planned visit 4), a virtual visit will take place and the TMS assessment will be omitted. During this virtual study visit, participants will complete surveys and PANESS remotely as described above and undergo a research physical exam/consultation with the study physician via telemedicine. At that point, the participant will discontinue study drug/placebo and officially conclude their participation in this study.

Contingency Option 2:

Study participants whom are currently enrolled and on study drug (or placebo) are to maintain a stable dose (no change in dose). If a participant has an essential clinic visit during or after week 18 of this study (the point of a typical visit 4), the family and research team may consider conducting the week 18 research visit with significant contact restrictions. An essential clinic visit will be defined as a clinic visit that has not been rescheduled as part of the current hospital restrictions. While on campus for an essential clinic visit, participants will receive visit 4 safety labs/EKG and TMS. All assessments that can be done remotely (surveys, PANESS, telemedicine physical exam) will be done remotely as described under contingency 1.

Precautions will be taken to minimize potential exposure. The study coordinator will review the current pre-visit mandates outlined on Centerlink with the participant/family. Communication via email or phone will be made the day prior to the study visit to confirm that the participant and parent are healthy (symptom free). If the participant or any member of their household has a fever, cough or colds, body aches, or stomach virus symptoms, the study visit will be cancelled and contingency option 1 will be implemented. Only one family member (a parent/guardian and no siblings) will be permitted on campus with the study participant. Additional restrictions will be implemented as appropriate per hospital and government policy/recommendations.

CLINICAL SUICIDE IDEATION PLAN:

Rationale:

Per FDA Guidance for Industry: Suicidal Ideation and Behavior: Prospective Assessment of Occurrence in Clinical Trials, an assessment for suicide will be performed at each visit.

Suicide assessment:

Columbia Suicide Severity Rating Scale, C-SSRS

Review of C-SSRS Responses:

Study doctor (or designee) will verbally administer and then review each suicide assessment. The 'Columbia-Suicide Severity Rating Scale Screen with Triage Points' document outlines the planned course of action based on the participant's response. In particular, if a participant discloses any suicide

Version 9.0 MAR2020 Page **10** of **24**

ideation, the study staff will contact the participant's mental health provider or PCP and/or *Psychiatric Intake Response Center (PIRC)* at Cincinnati Children's Hospital for further assessment and guidance.

The Pediatric Intake Response Center (PIRC) manages psychiatric patient consultation and intake for Cincinnati Children's Hospital Medical Center. Staff members are available 24 hours a day, seven days a week at [contact] or [contact].

DURATION:

The current plan is for the study to last for 3 years. Data analysis and completion of study reports/papers will occur in the last 6 months of the study (see timeline below).

Timetable					
Sept 2018	IRB submission				
Oct 2018 – Jan 2018	Operations Staff Preparation/ Prepare materials for Orientation and Training				
	Meeting; CRF Dataform Generation; Prepare Study Medication Packets and				
	Materials for Study Initiation				
Feb 2018 - Jun, 2019	First Subjects recruited				
June 2019 - Aug, 2020	Subjects recruited, complete the study				
Sept 2020 - Dec 2020	Data closeout and analysis, submit manuscript				

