Table 3: SCHEDULE OF STUDY VISITS									
	Visit 0 Screening	Visit 1 Initiation Phase I	Remote monitor and safety	Visit 2 End Phase I	Interphase (No meds)	Visit 3 Initiation Phase II	Remote monitor and safety	Visit 4 End Phase II	Visit 5 Debrie fing Intervi ew
Task	Week -1	Week 0	Week 4	Week 8	Week 9-10	Week 10	Week 14	Week 18	
Review Eligibility Criteria	X								

Version 9.0 MAR2020 Page **15** of **24**

Informed Consent	X							
KSADS PL Interview	X							
KBIT-2 (Kaufman Breif Intelligence Test, Second Edition).	X							
MRI (optional)**	X							
PARS (Pediatric anxiety rating scale)	X		X	X	X	X	X	
CDRS (Children's depression rating scale)	X		X	X	X	X	X	
Physical Exam*	X	X		X	X		X	
Vitals*	X	X		X	X		X	
Urine Pregnancy (Females only)	X	X			X			
C-SSRS (Columbia Suicide Severity Rating Scale)	X	X	X	X	X	X	X	
ADHD-RS (DuPaul) - Parent		X	X	X	X	X	X	
Safety labs*		X		X	X		X	
TMS assessment		X		X	X		X	
Med Log		X	X	X	X	X	X	
NAC/Placebo Prescription		X			X			
PANESS scale		X		X	X		X	
Metabolomics		X		X	X		X	
Behavioral Rating Inventory of Executive Function (BRIEF) - Parent (optional)		X		X	X		Х	
AE assessment (MedDRA)		X	X	X	X	X	X	X
Follow-up plan				X				X

^{*} Indicates clinical procedures performed as standard of care

Treatment with NAC: For this double-blind placebo controlled study without dose modification of NAC, each subject will be dosed with 70 mg/kg/dose (max dose 900 mg) three times per day of NAC for 8 weeks. The maximum daily dose will be 2700 mg (900 mg per dose, three times per day). We have treated 5 patients off-label with NAC at 900 mg twice daily with improved behaviors without side effects. NAC is a natural supplement that acts as an antioxidant and a glutamate modulating agent. It is widely available over the counter.

Monitoring and Managing Adherence to Treatment:

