16. COST OF PARTICIPATION

There will be no charges to participants or to third party payers related to study visits or procedures in this study. NAC is an FDA approved medication. NAC will be provided for the 8 week duration of the study to all participants.

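### The Phase I text sets a 1-week drug-free interphase, but the visit schedule with two 8-week phases nominally gives 2 weeks

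*Combined protocol and SAP*

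**What the plan says.** The Phase I text (Treatment Observation Period) has children stop medication at the end of Visit 2 and go through an interphase "for 1 week during which they will abstain from medication", after which they begin the alternate arm. The same paragraph states that "A repeat longitudinal TMS study will occur at weeks 8 and 18" and identifies those weeks as the ends of the two phases.

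Table 3 (Schedule of Study Visits) counts from week 0 at Visit 1. It gives Visit 2 at week 8, a no-medication interphase column at weeks 9-10, Visit 3 at week 10, the second remote monitoring at week 14 and Visit 4 at week 18. The section on Visits 1 and 3 starts dosing at the end of each of those visits.

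The plan fixes the length of a phase in several places. Treatment with NAC sets dosing "three times per day of NAC for 8 weeks". Section 16 says that "NAC will be provided for the 8 week duration of the study to all participants". The section on Visits 2 and 4 places TMS after 8 weeks of NAC or placebo. Overview of Design makes the two phases alike in everything except the arm.

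The Emergency Study Extension uses the same calendar. It describes active children as follows: "all are currently in phase II of the study, between week 14 and 18". It also refers to "week 26 (8 weeks after the originally-planned visit 4".

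**The concern.** The washout is an operating figure of a crossover trial, not background text. Here the narrative gives one length and the visit calendar another, and a site cannot follow both.

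The interval bears on the analysis through Visit 3. The plan repeats TMS, PANESS and the ADHD rating at that visit, just before Phase II dosing. Any NAC effect still present then could occur only in children who had NAC first. The Statistical Analysis section plans paired t tests before and after treatment without saying which visit is the before value for Phase II. If it is Visit 3, the washout length affects the Phase II change score differently in the two sequences. Those t tests alone also do not compare NAC with placebo, and the mixed models are described with subject-specific random effects but with no named treatment or period term.

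**Working it through.** **Inputs.** From Table 3: Visit 1 at week 0, monitoring at 4, Visit 2 at 8, Visit 3 at 10, monitoring at 14, Visit 4 at 18. From the Phase I text: 1 week off drug, and phase ends at weeks 8 and 18. From Overview of Design, Treatment with NAC and the Visit 2 and 4 section: 8 weeks per phase. From the section on Visits 1 and 3: dosing restarts at the end of Visit 3. From the Emergency Study Extension: week 26 is 8 weeks after the planned Visit 4.

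**1. Attempt to reproduce the stated 1 week.** Off-drug interval = Visit 3 − Visit 2 = 10 − 8 = 2 weeks. The stated figure is not reproduced.

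**2. Cross-check without Visit 3.** End of Phase II − end of Phase I − length of Phase II = 18 − 8 − 8 = 2 weeks. This uses the Phase I text's own weeks 8 and 18, so that paragraph conflicts with itself.

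**3. Spacing within phases under the schedule.** Start to monitoring: 4 − 0 = 4 and 14 − 10 = 4. Start to end: 8 − 0 = 8 and 18 − 10 = 8. The phases match, as the design overview requires.

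**4. Is week 18 a slip?** 26 − 8 = 18, so the contingency text independently confirms it.

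**5. What 1 week off would require with 8-week phases.** Visit 3 at 8 + 1 = 9, monitoring at 9 + 4 = 13, Visit 4 at 9 + 8 = 17.

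| Time point | Schedule (2 weeks off) | With 1 week off |
|---|---|---|
| Visit 2 | 8 | 8 |
| Visit 3 | 10 | 9 |
| Phase II monitoring | 14 | 13 |
| Visit 4 | 18 | 17 |

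**6. The other way to keep 1 week.** Holding Visit 4 at week 18 gives a Phase II of 18 − 9 = 9 weeks, against the 8 weeks stated throughout.

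**7. Size in days.** 2 × 7 = 14 against 1 × 7 = 7.

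**The case against.** **Week labels are not exact days.** If week 8 and week 10 name study weeks rather than points, a visit late in week 8 and one early in week 10 leave about 1 week between them, and the interphase label of weeks 9-10 could be read alone as one week. This stands in part, and it is why the result is stated as nominal. It does not rescue the text: the interphase begins at Visit 2, drug restarts at Visit 3, and the table counts from week 0 with equal spacing in both phases.

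**The schedule already answers the question.** One phrase is the outlier, and a site working from Table 3 would use 2 weeks. That is fair, and it makes the correction easy. It does not make the current text right.

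**The analysis remedy is a separate matter.** Missing treatment and period terms would be a weakness with either washout. That is true, but an end-of-phase contrast is also what frees the comparison from the Visit 3 value, so it belongs with the fix.

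**The pandemic extension is larger.** Dosing may continue to as late as week 26, which would make Phase II 26 − 10 = 16 weeks on the schedule. This stands: it outweighs a one-week discrepancy, and any tabulation or contrast must allow for it.

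**A tempting stronger reading.** A reader might infer that Phase II ran 9 weeks, so that placebo-first children received more NAC than NAC-first children. The documents do not support this. It needs a 1-week washout combined with Visit 4 at week 18, which the 8-week dosing, the 8-week supply, TMS after 8 weeks and the matching phases all contradict.

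**Conclusion.** The inconsistency is real and lies in the current text. The schedule nominally gives 2 weeks off drug where the narrative gives 1: 14 days against 7, with the Phase II time points one week later than a 1-week interphase would put them. This rests on reading the week labels as nominal time points and on both phases lasting 8 weeks.

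A reader might also infer that a short washout biases the results. The documents do not show this. They give no rate at which a NAC effect fades, do not say that Visit 3 serves as the Phase II baseline, and do not record which interval was used. A residual effect at Visit 3 would matter only if that value enters the comparison. No sample size is affected, because the plan makes no such calculation.

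The point is therefore a modest one: an operating figure to correct, and an analysis to specify so that the answer depends less on it.

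**What to change.** 1. In the Phase I text, change the interphase from one week to two for any child yet to reach it.
2. For all other children, do not restate the interval after the fact. Derive actual off-drug days and Phase II days on treatment from visit dates and medication logs, including time under the Emergency Study Extension, and report them per child.
3. Base the NAC–placebo comparison on the within-child contrast of end-of-phase scores, Visit 2 against Visit 4, with treatment and period as named terms in the mixed model. A Visit 3 value that may carry residual NAC effect is then not subtracted. This does not remove an effect still present at Visit 4, 18 − 8 = 10 weeks after Phase I ends.
4. For children under the contingency plan, use the week-18 assessment as the end-of-Phase-II value where it exists, and label later assessments, such as delayed TMS, as late.

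**Cost.** One wording change, one tabulation and one named contrast, with no new procedures. The data are ones the protocol already plans to collect, though Visit 4 is still pending for active children. The wording change has limited reach: all active children are already in Phase II, and a new child would have to start by about 27 April 2020 to complete 18 weeks (126 days) by 31 August 2020, the end of the timetable's recruitment and completion period.
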